14.2.7 Patient Reported Outcomes

There are three PRO questionnaires expected to be filled in by the participants at each of the scheduled assessments: EQ-5D-5L, EORTC QLQ-C30 and NSCLC-SAQ. Results will be presented as described in Sections 8.1.1 and 8.1.2, but only for the combination arm. Data collected will be listed for both treatment arms.

For the definition of baseline, the same rules specified in Section 9.4 will be applied.

Questionnaires collected at the end of treatment (EOT) visit or at the safety follow-up (Safety FU) visit will be pooled together because, in clinical practice, only one out of two is usually completed. In the event both are completed, the earlier will be considered for descriptive summaries as well as for the longitudinal analysis.

For each questionnaire, the change from baseline of dimension/domain scores as well as total scores will be presented using box and whiskers plots.

Only visits available for more than 10 participants will be included in tables and plots; on the other hand, the EOT/Safety FU visit will always be presented.

Questionnaire Completion

For each questionnaire and scheduled visit (i.e. Baseline, Cycle 3 Day 1, Cycle 5 Day 1, etc, EOT/Safety FU), the following will be summarized:

- Number and percentage of participants with an expected questionnaire
- Questionnaire completion: Number and percentage of participants who completed the questionnaire. Percentages will be calculated twice, as:

% Questionnaire Completion

 $= 100 \times \frac{number \ of \ subjects \ with \ all \ questionnaire \ items \ available}{number \ of \ subjects \ for \ whom \ the \ questionnaire \ is \ expected}$

and

% Questionnaire Completion

 $= 100 \times \frac{\text{number of subjects with all questionnaire items available}}{\text{number of subjects in the respective analysis set}}$

Number and percentage of participants who did not complete the questionnaire, by reason for non completion.

• Questionnaire compliance: Number and percentage of participants with an evaluable questionnaire, i.e., scores for each dimension/domain can be calculated.

% Compliance =
$$100 \times \frac{number \ of \ subjects \ with \ evaluable \ question naire}{number \ of \ subjects \ for \ whom \ the \ question naire \ is \ expected}$$

and

% Compliance = $100 \times \frac{number \ of \ subjects \ with \ evaluable \ questionnaire}{number \ of \ subjects \ in \ the \ respective \ analysis \ set}$

Of note, the number of participants with an expected questionnaire, according to the protocol schedule of assessments, will be used as denominator for percentages. A questionnaire is expected in the following cases:

- the participant attended a scheduled visit where the questionnaire was required to be completed;
- the participant missed a visit where the questionnaire was required to be completed but he/she attended the following visit.

EQ-5D-5L

The EQ-5D-5L consists of 5 dimensions (Mobility, Self-Care, Usual Activities, Pain/Discomfort and Anxiety/Depression) and each dimension has 5 levels: no problems (1 = best), slight problems (2), moderate problems (3), severe problems (4), and extreme problems (5 = worst). In addition, participants will provide a global assessment of their health through the EQ VAS score: it goes from 100 (best imaginable heath) to 0 (worst imaginable health).

Baseline, post-baseline and change from baseline values of the EQ VAS score will be summarized at each time point. The number and percentage of participants whose score has improved, not changed or worsened will also be presented.

For each participant, EQ-5D-5L dimension scores and the EQ VAS score over time will be listed.

EORTC QLQ-C30 (Version 3.0)

Each of the 15 component scores will be derived as the mean of all items within that component standardized to a 0 to 100 scale as described below for the specific sub-dimension that the component belongs to. If more than 50% of the items within a component are missing then the score for that component will be set to missing, otherwise the mean of non-missing items will be calculated. Table 7 contains the instructions to be followed to calculate the scores.

63/94

Baseline, post-baseline and change from baseline values in each sub-dimension will be summarized at each time point. The number and percentage of participants whose scores have improved, not changed or worsened will also be presented.

Listings of each item and sub-dimension scores over time will be provided for each participant.

Table 7. Scoring the QLQ-C30 (version 3.0)

	Scale	Number of items	Item range*	Version 3.0 Item numbers	Function scales
Global health status / QoL					
Global health status/QoL $(revised)^{\dagger}$	QL2	2	6	29, 30	
Functional scales					
Physical functioning (revised) [†]	PF2	5	3	1 to 5	F
Role functioning (revised) [†]	RF2	2	3	6,7	F
Emotional functioning	EF	4	3	21 to 24	F
Cognitive functioning	CF	2	3	20, 25	F
Social functioning	SF	2	3	26, 27	F
Symptom scales / items					
Fatigue	FA	3	3	10, 12, 18	
Nausea and vomiting	NV	2	3	14, 15	
Pain	PA	2	3	9, 19	
Dyspnoea	DY	1	3	8	
Insomnia	SL	1	3	11	
Appetite loss	AP	1	3	13	
Constipation	CO	1	3	16	
Diarrhoea	DI	1	3	17	
Financial difficulties	FI	1	3	28	

* Item range is the difference between the possible maximum and the minimum response to individual items; most items take values from 1 to 4, giving range = 3.

† (revised) scales are those that have been changed since version 1.0, and their short names are indicated in this manual by a suffix "2" – for example, PF2.

For all scales, the *RawScore*, *RS*, is the mean of the component items: $RawScore = RS = (I_1 + I_2 + ... + I_n)/n$

Then for Functional scales:

$$Score = \left\{1 - \frac{(RS - 1)}{range}\right\} \times 100$$

and for Symptom scales / items and Global health status / QoL: $Score = \{(RS - 1)/range\} \times 100$

A higher score for a functional scale or for the Global Health Status indicates a more healthy level of functioning or higher quality of life, respectively; on the contrary, a high score for a symptom scale represents a high level of symptomatology.

NSCLC-SAQ (version 1.0)

Tepotinib (MSC2156119J)Tepotinib plus osimertinib in osimertinib-relapsed MET amplifiedMS200095-0031 (version 4.0)NSCLC

The NSCLC-SAQ consists of seven items covering five domains: Cough, Pain, Dyspnea, Fatigue, and Appetite. All five of these domains must be non-missing to compute a total score. Pain and Fatigue domains each contain two items.

Table 8 contains the instructions to be followed to calculate the score for each of the 5 domains as well as the total score. Higher scores indicate more severe NSCLC-related symptomatology.

Domain	Item		Response
Cough	1. How would you rate your coughing at its worst?		0, 1, 2, 3, 4
Pain	2. How would you rate the worst pain in your chest?3. How would you rate the worst pain in areas other than your chest?	Create a single score by selecting the highest severity (i.e., value) on either item	0, 1, 2, 3, 4
Dyspnea	4. How often did you feel short of breath during usual activities?		0, 1, 2, 3, 4
Fatigue	5. How often did you have low energy?6. How often did you tire easily?	Create a single score by calculating the mean of these 2 items	0, 1, 2, 3, 4
Appetite	7. How often did you have a poor appetite over the last 7 days?		0, 1, 2, 3, 4
NSCLC-SAQ Total Score (Sum the 5 domains)			Range 0 to 20

Table 8.Scoring the NSCLC-SAQ

If a respondent is missing any of the five domain scores, his or her NSCLC-SAQ total score will not be computed. If one of the Pain or Fatigue items is missing, the available item will be used as domain score; if both items are missing, the domain score will be set to missing.

Baseline, post-baseline and change from baseline values for each domain and for the total score will be summarized at each time point. The number and percentage of participants whose scores have improved, not changed or worsened will also be presented.

Listings of single items and sub-dimension scores over time will be provided.

Longitudinal analysis of change from baseline

A mixed-effect model repeated measures (MMRM) analysis will evaluate longitudinal change from baseline. This analysis will be performed on the combination arm (mFAS) only. The following PRO scores will be analyzed:

- Cough (NSCLC-SAQ; item 1)
- Pain (NSCLC-SAQ; items 2 and 3)
- Dyspnea (NSCLC-SAQ; item 4).

A distinct MMRM will be run for the T+, L+ and Combined (T+ and/or L+) participants in the combination arm. The model will include change from baseline as a dependent variable and analysis visit (as defined in Section 9.8) and baseline PRO score as covariates and baseline PRO score by analysis visit interaction to account for a non-constant baseline effect across visits.

An unstructured covariance matrix will be used to model the within-subject error. In case the fit fails to converge or if convergence is unreliable (e.g. problems to make hessian matrix positive definite), the best variance-covariance pattern will be chosen based on the model fit using the Akaike's Information Criterion among Toeplitz, first-order autoregressive and variance components. The model will use restricted maximum likelihood (REML) to provide an overall adjusted mean estimate that will estimate the average treatment effect over visits giving each visit equal weight. The Kenward-Roger approximation will be used to estimate the degrees of freedom. No p-values will be presented. No subgroup analysis planned.

Least square (LS) means estimates and corresponding 95% CIs will be presented overall, to provide an estimate of the treatment effect across visits, and at Day 85 (Week 12, i.e. Cycle 5 Day 1), Day 169 (Week 24, i.e. Cycle 9 Day 1), Day 253 (Week 36, i.e. Cycle 13 Day 1), Day 337 (Week 48, i.e. Cycle 17 Day 1), Day 421 (Week 60, i.e. Cycle 21 Day 1) and every 12 weeks thereafter. Additionally, a line plot will be produced.

Technical details on the analysis described above are available in Appendix 5.

The week 12 assessment collected at Cycle 5 Day 1 is considered a key timepoint for comparative PRO evaluations. This time point would minimize loss of data due to deaths and disease progression and most participants are expected to be still exposed to treatment. Changes in symptoms as reported by the participants may manifest or likely occur at that time-point.

It is anticipated that the key symptoms pain, cough and dyspnea might remain stable or improve within the first 12 weeks after treatment initiation. The threshold for maintenance should ideally correspond to the anchor based on published and validated Minimum Important Difference. If not available, Cohen's d will be calculated and an absolute threshold of 0.2 used as non-relevance threshold.

In order to calculate the Cohen's d, the following formula will be applied:

$$d = \frac{mean_{CHG}}{SD_{CHG}}$$

where

- $mean_{CHG}$ is the arithmetic mean of the change from baseline at Cycle 5 Day 1
- SD_{CHG} is the sample standard deviation of the change from baseline at Cycle 5 Day 1 calculated as follows

$$SD_{CHG} = \frac{1}{n-1} \sqrt{\sum_{i=1}^{n} (d_i - mean_{CHG})^2}$$

66/94

where n is the number of participants for which the change from baseline is not missing (i.e., both baseline and Cycle 5 Day 1 scores are available).

In addition, a bar chart presenting the change from baseline over time categorized as "Improved", "No change" "Worsened" will also be produced.

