Participants who withdraw from the study intervention for reasons other than PD or death will have additional visits for tumor assessments every 6 weeks until 9 months, and every 12 weeks

thereafter. A \pm 7-days time window is permitted for these additional follow-up visits until 9 months, and \pm 14 days thereafter. Reasons for study termination should be recorded if this visit is the last visit for the participant. Recording of any new anticancer therapy will be made (a tumor assessment is mandatory before initiating the new therapy).

Survival follow-up is to be performed every 3 months \pm 2 weeks at clinic visit or by telephone contact. Participants' survival information will be collected. Recording of any new anticancer therapy will be made until death. For patient reported outcomes (PROs) (EuroQol Five Dimension Five Level Scale [EQ-5D-5L], European Organization for Research and Treatment of Cancer Quality of Life Questionnaire Core 30 [EORTC QLQ-C30] and Non-small Cell Lung Cancer Symptom Assessment Questionnaire [NSCLC-SAQ]), the questionnaires will be completed at Screening (or at Day 1 of Cycle 1 prior to any other intervention or drug intake if it was missed at Screening) and every 6 weeks from Cycle 1, Day 1 until 9 months and every 12 weeks thereafter until disease progression, death, study withdrawal, or withdrawal of consent. At all visits indicated including EoT and Safety Follow-up, every effort should be made to have the questionnaires completed by the participant prior to the initiation of any other study activities (including RECIST Version 1.1 assessments) or active treatment and prior to any contact with the Investigator.

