18.5 Appendix 5 - SAS code for Longitudinal Analysis

Mixed Model for Repeated Measurements

The following example will be used a basis for the analysis:

run;

To derive mean_base the same approach used by SAS to derive standard least square (LS) means should be used, i.e. the average of BASE variable across all records included in the analysis (i.e., more than one record per subject). Of note, this is different from deriving the average of baseline values across subjects (i.e., only one record per subject). As an example, assuming there are analysis visits 1, 2 and 3 in the model and the average value of BASE across all records included in the analysis is 10.31, the following estimate statement should be used:

```
estimate "overall mean"
    intercept 1
    avisitn 0.333333 0.333333 0.333333
    avisitn*base 3.436663 3.436663 3.436663
    base 10.31/cl;
```

The first variance-covariance matrix that will be considered is the unstructured (type=un). If it fails to converge or the convergence is not reliable, the Toeplitz (type=toep), first-order autoregressive (type=ar(1)) and variance components (type=vc) will be tested. The matrix that provides a reliable convergence and has the smallest Akaike's criterion (AIC) provided by default by proc mixed will be selected.

Additionally, analysis visits with less than three participants will not be included in the analysis to avoid non convergence and non-estimability of LS means. This threshold may be increased if needed.

Signature Page for VV-CLIN-313940 v2.0

Approval Task

Signature Page for VV-CLIN-313940 v2.0

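### PRO mixed model: the fallback covariance list omits compound symmetry and keeps an independence structure; swapping the two is an optional, low-cost improvement

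*SAP*

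**What the plan says.** SAP 14.2.7 fits a repeated-measures model to change from baseline in three NSCLC-SAQ scores, in the combination arm only and separately for T+, L+ and the combined set. Terms are visit, baseline score and their interaction.

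- First choice: "An unstructured covariance matrix will be used to model the within-subject error".
- Trigger for the fallback: "In case the fit fails to converge or if convergence is unreliable".
- Fallback: selection by "Akaike's Information Criterion among Toeplitz, first-order autoregressive and variance components". Appendix 5 repeats the list ("the Toeplitz (type=toep), first-order autoregressive (type=ar(1)) and variance components (type=vc) will be tested") and gives the rule: "The matrix that provides a reliable convergence and has the smallest Akaike's criterion (AIC) provided by default by proc mixed will be selected".
- Target: an overall mean described as the "average treatment effect over visits giving each visit equal weight", with by-visit means and 95% intervals. "The Kenward-Roger approximation will be used to estimate the degrees of freedom".
- Sparse visits: Appendix 5 leaves out analysis visits with fewer than three participants and allows that threshold to be raised.
- Data: Protocol 8.1 collects questionnaires "every 6 weeks from Cycle 1, Day 1 until 9 months and every 12 weeks thereafter until disease progression". SAP 9.9 makes no general imputation.

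The estimand table in SAP section 14 names the least-squares mean changes for these three scores as an HRQoL summary. No p-values are planned.

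**The concern.** VC placed on the within-subject error sets the correlation between a participant's visits to zero. AR(1) lets the correlation die out with visit number. Neither holds a lasting difference between participants, which symptom scores commonly show. CS does so with two parameters and is not listed. Toeplitz can represent it, but needs one parameter per visit.

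Two things are at stake. The interval for the overall mean can be too narrow, and Kenward-Roger does not cure that because it is model-based. Also, nothing is imputed and questionnaires stop at progression, so protection against score-related dropout rests on the covariance model. If that model understates the correlation, the mean drifts towards apparent improvement. The rule operates in nine fits (three scores by three sets), some possibly in a set smaller than 80. The documents give no L+ total.

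**Working it through.** **Plan figures.** The documents state no correlation, SD or dropout rate for this model, so there is no precision figure to reproduce. The worked coefficient in Appendix 5 does reproduce: 0.333333 x 10.31 = 3.436663. This confirms the equal visit weights used below.

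**1. Parameters.** The schedule gives weeks 6, 12, 18, 24, 30, 36, 48 and 60, so 8 visits to Cycle 21. Unstructured needs 8 x 9 / 2 = 36 covariance parameters, Toeplitz 8, AR(1) 2, CS 2 and VC 1. Over 11 visits (to week 96) unstructured needs 66 and Toeplitz 11. Toeplitz with all bands equal is CS.

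**2. Is the fallback reachable?** With monotone dropout, an unstructured fit needs about T+2 participants at visit T. With 11 visits, exponential dropout and the three-participant rule (threshold not raised), the share of trials falling short is:

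| Assumed median time on study | n=80 | n=60 | n=40 |
|---|---|---|---|
| 40 weeks | 24% | 65% | 97% |
| 52 weeks | 1% | 12% | 70% |

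With 8 visits it is at most 6%. In 60 REML fits per cell (11 visits, exchangeable correlation 0.5 and 0.7), Toeplitz was unreliable in 0% at n=80 and in 13-20% at n=40.

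**3. VC in closed form.** For an equal-weight mean over T complete visits with exchangeable correlation rho, true SE / VC SE = sqrt(1 + (T-1) rho), and coverage = 2 Phi(1.96 / ratio) - 1. With T=8:

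| rho | Ratio | Coverage of a nominal 95% CI |
|---|---|---|
| 0.05 | 1.16 | 91% |
| 0.1 | 1.30 | 87% |
| 0.3 | 1.76 | 73% |
| 0.5 | 2.12 | 64% |
| 0.7 | 2.43 | 58% |

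**4. The rule as written.** The SAP model was simulated with 8 visits, REML, AIC = -2 REML logL + 2q and 300 trials per row. Assumptions: SD 1, monotone dropout more likely after a worse last score, and t = 1.99 in place of Kenward-Roger. Entries are coverage of the overall mean, with bias in SD in brackets where relevant.

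| n, true structure | VC chosen | SAP rule | SAP rule, Toeplitz unusable | CS in place of VC |
|---|---|---|---|---|
| 80, exch. 0.05 | 68% | 90.0% | 89.7% | 93.3% |
| 80, exch. 0.1 | 32% | 89.7% | 87.3% | 91.0% |
| 80, exch. 0.3 | 0% | 93.3% | 68.0% (-0.087) | 93.7% |
| 80, exch. 0.5 | 0% | 95.3% | 54.0% (-0.128) | 95.0% |
| 80, exch. 0.7 | 0% | 95.0% | 69.0% (-0.120) | 94.7% |
| 80, AR(1) 0.6 | 0% | 95.7% | 95.7% | 95.7% |
| 40, exch. 0.1 | 50% | 91.0% | 89.7% | 93.3% |
| 40, exch. 0.3 | 4% | 87.3% | 73.7% (-0.095) | 91.7% |

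The VC-chosen and last columns assume Toeplitz is usable. In the n=80 rows with correlation 0.3 or more, losing Toeplitz means AR(1) in every run, never VC. CS fitted alone covers 94-95% at 0.3 and 0.5.

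**5. Trials in which the rule chose VC.** At n=80, coverage was 88% (correlation 0.05) and 82% (0.1); at n=40 and 0.1 it was 83%. At n=40 and 0.3 it was 69%, but in only 13 runs.

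Monte Carlo error is about 1.3 points near 95% and 2.9 near 50%. The rule and its modification were scored on the same simulated trials.

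**The case against.** The strongest reply is that the plan has no step-down to VC. VC must have the smallest AIC among reliable fits, and Toeplitz already contains CS. This stands. At n=80 and correlation 0.5 the rule covers 95.3%, against 95.0% after the change.

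A reader might infer from step 3, or from forcing VC under score-related dropout (13% coverage and bias -0.206 SD at n=80, correlation 0.5), that the planned analysis would behave that way. The documents do not support this. At that correlation VC would be used only if both Toeplitz and AR(1) were unreliable, and how often that would happen cannot be derived from the documents.

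Other points that stand:

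- The sparse-visit threshold may be raised, which makes the fallback less frequent than step 2 suggests.
- A reader might compare these biases with the 0.2 non-relevance threshold in SAP 14.2.7. That threshold belongs to a Cohen's d built from the arithmetic mean and SD at Cycle 5 Day 1, so the covariance choice cannot move it.
- SAP 14.2.7 brings a pooled end-of-treatment or safety follow-up questionnaire into the longitudinal analysis. The simulations have no such record, so their dropout bias may be too large.
- The PROC MIXED call in Appendix 5 is not legible in the available copy. A random subject effect there would change what VC means.

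One part does not stand: that the listed set is enough in every case. It depends on Toeplitz being reliable, which is least assured in small sets with sparse late visits.

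**Conclusion.** The gap is real but narrow. With Toeplitz reliable, n=80 and correlation of 0.3 or more, nothing needs repair. The gap matters if Toeplitz is lost, when AR(1) covered 54-69% at n=80 under exchangeable correlation of 0.3-0.7. It also matters, more mildly, if correlation is weak or the set is small; there CS in place of VC gained about 1 to 4 points, a difference not far above simulation error.

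These sizes rest on assumed correlations, an assumed dropout mechanism and mostly exchangeable truth, which favours CS. Under a true AR(1) of 0.6 the change makes no difference. The analysis is descriptive, so no trial conclusion depends on it. This is an optional improvement.

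**What to change.** In SAP 14.2.7 and Appendix 5, replace variance components (type=vc) with compound symmetry (type=cs). The fallback set becomes Toeplitz, CS and AR(1), still chosen by AIC among fits that converge reliably.

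A sandwich standard error is not an adequate remedy for AR(1): it corrects the interval width and leaves the dropout bias in place.

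The cost is one phrase in each section and one SAS option, with no new data. CS has two parameters, as AR(1) does, so convergence should be no harder.

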Baseline brain metastases (Investigator)	PresentAbsent	This subgroup classifies participants according to whether or not they have target or non-target lesions in the brain as per investigator assessment. This information is collected on the "Tumor Assessment (according to RECIST 1.1) – Target Lesions" and "Tumor Assessment (according to RECIST 1.1) – Non-target Lesions" eCRF pages at baseline.
Histopathological classification	AdenocarcinomaSquamousOther	This information is collected in the "Histology" eCRF page.

Subgroup	Subgroup level	Definition/ Derivation
Clinical stage at study entry	AdvancedMetastatic	This information is collected in the "Disease History" eCRF page. The TNM classification at study entry will be used to derive the subgroup levels. See details in Section 18.2.
Time from metastatic disease diagnosis to first dose	 < 6 months ≥ 6 months 	The date of documented metastatic disease diagnosis collected in the "Disease History" eCRF page will be used.
Duration of prior osimertinib	 < 12 months ≥ 12 months 	Duration of prior osimertinib therapy (months) as first and only prior anti-cancer therapy. See Section 11.5 for more details.
Time from disease progression on prior osimertinib to first dose	 < 2 months ≥ 2 months 	Time from disease progression on prior osimertinib therapy as first and only prior anti-cancer therapy to start of study treatment (months). See Section 11.5 for more details.
Mean Gene Copy Number	• < 10 • ≥ 10 • < 8 • ≥ 8	Mean Gene Copy Number resulting from the analysis of tumor tissue samples performed centrally with the FISH test.
MET/CEP7 ratio	• <2 • ≥ 2 • $2-<4$ • ≥ 4	MET/CEP7 (centromere 7) ratio resulting from the analysis of tumor tissue samples performed centrally with the FISH test.
Smoking Status	Current SmokerFormer SmokerNever Smoker	Smoking status derivation can be found in Section 11.6.

9

General Specifications for Data Analyses

This section describes any general specifications not included in subsequent sections.

Presentation of continuous and qualitative variables:

Continuous variables other than PK will be summarized using descriptive statistics, i.e., the number of participants with non-missing values (n), mean, standard deviation, median, 25th percentile (Q1) and 75th percentile (Q3), minimum, and maximum.

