	 Population Level Summary: Median PFS time based on Kaplan-Meier estimates and 95% 2-sided CI Kaplan-Meier estimates 			
	 Sensitivity Analyses: As main estimand, but using Investigator assessment instead of IRC assessment. As main estimand but censoring participants who discontinued treatment due to COVID-19 before occurrence of an event at the time of event. 			
	 Supplementary Analyses: As main estimand and sensitivity analysis, but based on different populations: L+, T+ and/or L+. As main estimand, but considering the start of subsequent anti-cancer therapy as PD (composite strategy), to be repeated also on populations L+, T+ and/or L+. As main estimand and sensitivity analysis, based on tepotinib monotherapy as treatment., to be performed also on populations L+, T+ and/or L+. 			
OS	Endpoint: OS as measured by time from first study intervention to death			
	Population : as primary estimand			
	Treatment: Tepotinib combined with osimertinib, taking subsequent anti-cancer therapy int account			
 Intercurrent Event Strategy: Discontinuation of treatment: ignoring the intercurrent event (treatment-policy strat Start of subsequent anticancer treatment: ignoring the intercurrent event (treatment-strategy) 				
	 Population Level Summary: Median OS time based on Kaplan-Meier estimates and 95% 2-sided CI Kaplan-Meier estimates 			
	 Supplementary Analyses: As main estimand and sensitivity analysis, but based on different populations: L+, T+ and/or L+ 			
HRQoL	Endpoint: Change from baseline in health state as measured by the Visual Analogue Scale (VAS) as a component of the EQ-5D-5L questionnaire; global health status, sub-dimensions of functional scales and symptoms scales as measured by EORTC QLQ-C30; cough, chest pain, dyspnea, fatigue, appetitive and overall severity of symptoms measured by NSCLC-SAQ.			
	Population: as primary estimand			

Endpoint	Estimand Attributes			
	Treatment: as primary estimand			
	 Intercurrent Event Strategy: Discontinuation of treatment: ignoring the intercurrent event (treatment-policy strategy) Start of subsequent anticancer treatment: ignoring the intercurrent event (treatment-policy strategy) 			
	 Population Level Summary: LS Mean changes from baseline analysis for cough, pain and dyspnea (NSCLC-SAQ) General descriptive statistics to summarize values and change from baseline by visit 			

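### SAP 14.2.7 calls SD_CHG the sample standard deviation but prints SD/√(n−1); coded as printed, Cohen's d is inflated by √(n−1) and the fixed 0.2 threshold depends on n

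*SAP*

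**What the plan says.** The longitudinal part of SAP Section 14.2.7 treats Cycle 5 Day 1 (week 12) as a key timepoint for patient-reported outcomes and expects pain, cough and dyspnea to stay stable or improve by then. Its first choice of yardstick is an external one: "The threshold for maintenance should ideally correspond to the anchor based on published and validated Minimum Important Difference". If none is available, Cohen's d "will be calculated and an absolute threshold of 0.2 used as non-relevance threshold".

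Cohen's d is defined as d = mean_CHG / SD_CHG. The text then states that SD_CHG "is the sample standard deviation of the change from baseline at Cycle 5 Day 1 calculated as follows". The display that follows, in the extracted text, contains "1}{n-1} \sqrt{\sum_{i=1}^{n} (d_i - mean_{CHG})^2". In plain notation:

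SD_CHG (printed) = [1/(n−1)] × √[Σ(d_i − mean_CHG)²]

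where n counts participants with both a baseline and a Cycle 5 Day 1 score. The section presents these as the formulas to use.

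On presentation of the patient-reported outcomes, the same section says: "Results will be presented as described in Sections 8.1.1 and 8.1.2, but only for the combination arm". Those sections split the combination arm into T+, L+ and Combined.

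**The concern.** The words and the formula define two different quantities. The sample standard deviation has 1/(n−1) under the root; the printed version has it outside. No other part of the SAP settles the matter: Section 9 only names the standard deviation among the default summaries, and Appendix 5 covers only the mixed model.

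Cohen's d is meant to be free of sample size, so that 0.2 means a fifth of a standard deviation however many participants contribute. As printed, d grows with n while the threshold stays fixed. Three things would follow:

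- A symptom that had not changed would usually be reported as having moved beyond the non-relevance threshold, in one direction or the other.
- The effective cut would differ between T+, L+ and Combined simply because these groups differ in size.
- The reported d would disagree with mean/SD from the study's own change-from-baseline table.

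**Working it through.** **Inputs**

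- Printed SD_CHG, d = mean_CHG/SD_CHG, the definition of n and the 0.2 threshold: SAP Section 14.2.7.
- n at Cycle 5 Day 1: not given in either document. Assumed values are 20, 40, 60 and 80; the last is the planned size of the T+ combination set (Protocol Section 9.2).
- The documents give no numerical SD or d, so there is no figure of the plan's own to reproduce.

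**Step 1: the factor**

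Let SS = Σ(d_i − mean_CHG)².

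- Sample SD = √[SS/(n−1)] = √SS / √(n−1)
- Printed SD_CHG = √SS / (n−1) = sample SD / √(n−1)
- Hence printed d = √(n−1) × mean/SD

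The ratio of sample SD to printed SD_CHG was also computed on simulated change scores for several n between 11 and 120 and equalled √(n−1) each time.

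**Step 2: what the printed d measures**

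The one-sample t statistic is T = √n × mean/SD, so printed d = T × √[(n−1)/n]. It behaves as a test statistic, not an effect size.

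**Step 3: effect on the threshold**

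A printed d of 0.2 corresponds to mean/SD = 0.2/√(n−1). A mean/SD of exactly 0.2 would be reported as 0.2 × √(n−1).

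| n | Inflation √(n−1) | mean/SD at which printed d = 0.2 | Printed d when mean/SD = 0.2 |
|---|---|---|---|
| 20 | 4.36 | 0.046 | 0.87 |
| 40 | 6.24 | 0.032 | 1.25 |
| 60 | 7.68 | 0.026 | 1.54 |
| 80 | 8.89 | 0.023 | 1.78 |

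Example: a mean/SD of 0.03 gives a printed d of 0.03 × 4.359 = 0.13 at n = 20, below the threshold, and 0.03 × 8.888 = 0.27 at n = 80, above it. The correct d is 0.03 in both cases.

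**Step 4: how often an unchanged symptom crosses the threshold**

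With true mean change 0 and normal changes, T has a t distribution with n−1 degrees of freedom.

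- Printed d is beyond ±0.2 when T is beyond ±0.2 × √[n/(n−1)].
- Correct d is beyond ±0.2 when T is beyond ±0.2 × √n.

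| n | Probability beyond ±0.2, as printed | Probability beyond ±0.2, correct SD |
|---|---|---|
| 20 | 0.840 | 0.382 |
| 40 | 0.841 | 0.213 |
| 60 | 0.841 | 0.127 |
| 80 | 0.841 | 0.078 |

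**Step 5: without normality**

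The symptom scores are coarse, so the check was repeated by simulation with 200,000 samples per n. Changes of −2, −1, 0, 1 and 2 were given probabilities (0.08, 0.22, 0.40, 0.22, 0.08) or (0.04, 0.16, 0.60, 0.16, 0.04); both distributions are assumptions. As printed, the probability of crossing ranged from 0.813 to 0.882. With the correct SD it was 0.376 and 0.397 (n = 20), 0.215 and 0.218 (n = 40), 0.126 and 0.128 (n = 60), and 0.077 for both (n = 80).

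**The case against.** The best answer is that this is a typesetting slip in a correctly named statistic. Sample standard deviation has one usual meaning, the n−1 divisor is present, and only the reach of the radical is wrong. A programmer would probably take the SD that SAS already produces for the planned summaries, so the figures above describe a coding error that may never happen. They also rest on assumed values of n and assumed change distributions.

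The equation was also read from a PDF. Another one, creatinine clearance in SAP Section 15.4, is visibly damaged in the extracted text.

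The role is small as well. Cohen's d is a fallback behind a validated Minimum Important Difference, it feeds a descriptive judgement, and no study decision depends on it. The HRQoL estimand in SAP Section 14 is summarised by "LS Mean changes from baseline analysis for cough, pain and dyspnea (NSCLC-SAQ") and by descriptive statistics, not by d. Finally, a d inflated four- to nine-fold would stand out beside the tabulated mean and SD.

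Much of this stands: it limits the scope and makes literal coding less likely to go unnoticed. It does not remove the contradiction. The SAP gives an explicit formula, and someone programming independently from it would get a different d. If the production program uses the ordinary SD, the SAP misdescribes the output and still needs correcting. The extracted expression for SD_CHG is well formed, and the radicals in Sections 11.6 and 15.6.2 came through correctly. An extraction fault is therefore possible but not shown, and a look at the original page settles it.

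**Conclusion.** The concern holds. As the text reads, SD_CHG is labelled as one quantity and computed as another, and the factor √(n−1) between them is exact.

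The practical size depends on the formula being coded literally and on n. For 20 to 80 paired scores, d would be inflated 4.4- to 8.9-fold. An unchanged symptom would cross the 0.2 threshold about 84% of the time under normality, or 81% to 88% under the whole-point distributions tried. With the correct SD the figures fall from about 38–40% at n = 20 to 8% at n = 80.

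The consequence is confined to the fallback week-12 maintenance judgement on three symptom scores in the combination arm. The documents do not say whether a validated Minimum Important Difference exists, so whether the fallback will be needed is unknown. The mixed model, the HRQoL estimand summaries, the primary response rate and the sample size are untouched. It should be fixed because a stated analysis rule is wrong as written and the repair is trivial.

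**What to change.** First check the position of the radical on the original page of SAP Section 14.2.7. If it is as extracted, replace the formula with

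SD_CHG = √{[1/(n−1)] × Σ(d_i − mean_CHG)²}

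and keep d = mean_CHG/SD_CHG and the 0.2 threshold. A different symbol for the individual changes would avoid using d for two things.

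Then confirm that the analysis program and any existing outputs use the corrected form. The material is already planned: for the NSCLC-SAQ, "change from baseline values for each domain and for the total score will be summarized at each time point", and the default continuous summaries in SAP Section 9 include "the number of participants with non-missing values (n), mean, standard deviation, median". Reported d at Cycle 5 Day 1 should equal mean/SD from that table in each of T+, L+ and Combined for which d is reported.

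The cost is one corrected formula and one program check, with no new data or analysis.
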